5.2.4 AD Sub-Study stimulation parameters

This protocol involves repetitive TMS at a frequency of 10 Hz. According to establish guidelines, the maximum safe duration of single trains of rTMS at 10 Hz using an intensity of 110% of MT is >5 seconds (106). Working well within these guidelines, we will be administering 2 second trains at 100% of MT. There will be 30 trains delivered to each of the two stimulation locations, with a 30s inter-train interval.

Prior to administering experimental TMS, we will determine the motor threshold (MT) of each patient by stimulating the motor cortex in the unaffected hemisphere. MT will be defined as the minimum percentage of machine output required to produce MEPs of at least 50 microVolts on at least 5 of 10 consecutive trials at the same location. MT will be determined by single-pulse

stimulation of the motor cortex subserving the contralesional hand at a suprathreshold level and subsequently reducing the percentage of the machine output until MEPs are not identified. The coil will be placed with the handle pointing to the patient's back at about 45° from the vertical position. Following determination of MT, patients will undergo 10 Hz rTMS.

The sham TMS group will be treated in the same manner as the experimental group except that MT will not be determined for the sham group. Thus, subjects in this group will never receive TMS. Sham treatment will employ a sham coil that produces the same sound as the real coil. Additionally, surface electrodes will be placed on the scalp, which will simulate the sensation of TMS. The sham and real coils will be numbered and the coil used and the MT will be recorded for each session.

5.2.5 Constraint Induced Language Therapy (CILT)

CILT is a commonly used form of speech therapy. CILT will be delivered immediately after TMS to take advantage of the "state-dependent" effects of TMS. In our version of CILT, a Speech Pathologist (or research personnel trained under the supervision of our Speech Pathologist) will function as both conversational partner and therapist-coach. In each session, the patient and SLP will start with identical decks of treatment card. Seated across a 30-cm. barrier, each will array their cards 6 at a time. Choosing a card from his/her array, the participant will call for its match using a verbal description (e.g., at the HFA level: "throw the ball"). If the description is incorrect or insufficiently precise to specify the target, the SLP will view the participant's card and supply cues to its description, using the Boston Naming Test cueing hierarchy: semantic, followed by phonologic, followed, after ~5 seconds, by repetition of the target word or phrase. Non-verbal expressions of the target, though not prohibited, will not be accepted as a substitute for the verbal response. The SLP will then take a turn, and request a card from the subject. Once all 6 cards are gone, the next 6 cards will be set up and the protocol repeated. On each trial, the SLP will score accuracy and type/amount of cuing needed to generate the response.

Each session will last 60-90 minutes, depending on the pace of participants' responses. If a person finishes a particular stimulus set in less than 45 minutes of therapy, the SLP will repeat the same stimulus subset from the easiest category.

Stimuli for the CILT protocol will include 2 different sets of 48 cards. Each set will contain 12 exemplars of 4 categories: High Frequency nouns (HFO); Action/Function verbs associated with the HFO (HFA); Low Frequency nouns (LFO); Action/Function verbs associated with the LFO (LFA). To avoid biasing performance on the primary outcome measure (WAB), there will be no overlap between the CILT stimuli and the stimuli of the WAB. We will also minimize overlap with items on the PNT.

The two 48-item sets will be used to select treated and untreated items, as follows. Each set will be presented twice in the baseline sessions (see Fig. 1), with participants scored on their ability to name the image and use the name in a sentence. Phonemic, semantic, self-correction, and no response errors will be coded from audio transcripts. If accuracy on one or more categories varies substantially between the sets (i.e. greater than 20% difference) the sets will be redistributed to match accuracy and, to the degree possible, error type. One set will be used for the treatment phase of the study; the other will be untreated and will provide a measure of generalization.

Scores on the pre-treatment baselines will be used to set the starting point for CILT treatment, using an 80% criterion. For example, if the participant's baseline performance is > 80% accurate for HFO production but < 80% for HFA, then treatment will begin at the level of HFA and will remain at this level of difficulty until the 80% is met in two successive sessions.

5.3 Blinding

Participants will not be informed of their assignment to active or sham status. Sham TMS will be administered with a sham TMS coil that looks and sounds like the active coil but does not generate a magnetic field. Surface electrodes applied to the scalp during sham stimulation will simulate the sensation of TMS, therefore allowing subjects with prior experience with TMS to be blind to condition as well.

The unblinded study coordinator will keep the master file of subject assignments. This individual will administer TMS, but all other individuals in contact with the subject or their data will be unaware of group assignment. In particular, the speech-language pathologist (SLP) and the individuals administering and scoring the language measures will not be present for the administration of TMS and will be blinded with respect to subject assignment. In the case of an adverse event, the blind may be broken if the PI deems it necessary.

5.4 Administration and Accountability

All stimulation sessions will be logged in a TMS log that will be kept in a secure location in the lab space. This log will include the date of stimulation, the individual administering TMS, and the MT of the patient as percentage of machine output.

5.5 Subject Compliance Monitoring

Noncompliance with regard to the randomized intervention could occur if participants miss therapy sessions or if the wrong coil is used to administer TMS. To minimize noncompliance due to missed therapy sessions, participants who miss up to 3 sessions will be allowed to make up missed sessions the following week. To avoid error in coil selection, sham and active TMS coils will be labeled numerically, and TMS technicians will be asked to record the number of the coil used in each administration of TMS in the TMS log.

6 Study Procedures

6.1 Screening

The screening visit will consist of:

- Informed Consent
- Review of the Inclusion/Exclusion Criteria
- Review of Demographics/Medical History
- Medical Intake (performed by the study PI or [name], both of whom are neurologists).
- In cases where the baseline visits will be conducted via tele-assessment, the Ruff Figural Fluency test may be administered at this visit.

The anticipated time of this visit is 30 minutes; depending on the subject's interest and responses to the screening tests, this visit could be combined with Visit 1 below.

An initial remote screening visit may be conducted via Bluejeans. Before screening and the medical intake, remote consent will be obtained, with e-signatures collected via RedCAP (explained in detail below). An in-person Medical Intake screening may occur after the remote consent and screening.

At the time of screening, or sometime afterwards, the Aphasia Depression Rating Scale (ADRS) will be completed by the patient's caregiver. The caregiver rates the subject on 9 different items. The ADRS has high reliability, sensitivity and specificity and is specifically designed for evaluation of aphasic patients (147). The ADRS will be given to the patient's caregiver to complete at the

time of screening, or will be mailed to the caregiver or close relative before the baseline screening. The ADRS will serve as a covariate in statistical analysis.

6.2 AD Sub-Study Screening

The screening visit will consist of:

- Informed Consent
- Review of the Inclusion/Exclusion Criteria
- Review of Demographics/Medical History
- Medical Intake (performed by the study PI or [name], both of whom are neurologists).
- 15 item Geriatric Depression Scale (GDS): This test requires the subject to answer “yes” or “no” to convey symptom presence/absence over the past week. The GDS has good reliability, sensitivity, and specificity for older persons.
- The Mini-Mental State Exam (MMSE)
- In cases where the baseline visits will be conducted via tele-assessment, the Ruff Figural Fluency test may be administered at this visit.
-

The anticipated time of this visit is 30 minutes; depending on the subject’s interest and responses to the screening tests, this visit could be combined with Visit 1 below.

An initial remote screening visit may be conducted via Bluejeans. Before screening and the medical intake, remote consent will be obtained, with e-signatures collected via RedCAP (explained in detail below). An in-person screening visit for in-person Medical Intake, GDS, and MMSE may take place after the remote consent and screening.

6.3 Study Intervention Phase

6.3.1 Visit 1 (Baseline 1)

- Western Aphasia Battery
- Philadelphia Naming Test
- Pyramids & Palm Trees
- Communication Confidence Rating Scale for Aphasia
- CILT Baseline Assessment
- Genetic testing: A saliva sample will be collected to determine the gene polymorphism for brain derived neurotrophic factor (BDNF)

The anticipated time of this visit is 120-180 minutes. Testing that is not finished in this visit will be continued in the second Baseline visit.

Baseline visits might be conducted via tele-assessment, using Bluejeans, or a HIPAA compliant alternative. In such cases, testing materials may be mailed to participants beforehand, and instructions provided during the tele-assessment. Other test materials will be displayed over the video software. Video and audio of the tele-assessment will be recorded. The genetic sample will not then be collected during virtual assessment.

6.3.2 Visit 1 (Baseline 1) for AD Sub-Study

- Western Aphasia Battery
- Philadelphia Naming Test
- Pyramids & Palm Trees

- Communication Confidence Rating Scale for Aphasia
- CILT Baseline Assessment
- Semantic fluency
- Genetic testing: A saliva sample will be collected to determine the gene polymorphism for brain derived neurotrophic factor (BDNF)

The anticipated time of this visit is 120-180 minutes. Testing that is not finished in this visit will be continued in the second Baseline visit

Baseline visits might be conducted via tele-assessment, using Bluejeans, or a HIPAA compliant alternative. In such cases, testing materials may be mailed to participants beforehand, and instructions provided during the tele-assessment. Other test materials will be displayed over the video software. Video and audio of the tele-assessment will be recorded. The genetic sample will not then be collected during virtual assessment.

6.3.3 Visit 2 (Baseline 2)

- Western Aphasia Battery
- Figural Fluency
- Word and Non-word repetition
- Cinderella Story
- CILT baseline

The anticipated time of this visit is 120-180 minutes. Testing that is not finished in this visit will be continued in the third Baseline visit.

Baseline visits might be conducted via tele-assessment, using Bluejeans, or a HIPAA compliant alternative. In such cases, testing materials may be mailed to participants beforehand, and instructions provided during the tele-assessment. Other test materials will be displayed over the video software. Video and audio of the tele-assessment will be recorded. The genetic sample will not then be collected during virtual assessment.

6.3.4 Visit 2 (Baseline 2) for AD Sub-Study

- Western Aphasia Battery
- Figural Fluency
- Word and Non-word repetition
- Cinderella Story
- Repeatable Battery for the assessment of Neuropsychological Status (RBANS)
- CILT baseline

The anticipated time of this visit is 120-180 minutes. Testing that is not finished in this visit will be continued in the third Baseline visit.

Baseline visits might be conducted via tele-assessment, using Bluejeans, or a HIPAA compliant alternative. In such cases, testing materials may be mailed to participants beforehand, and instructions provided during the tele-assessment. Other test materials will be displayed over the video software. Video and audio of the tele-assessment will be recorded. The genetic sample will not then be collected during virtual assessment.

6.3.5 Visit 3 (Baseline 3)

Baseline testing that is not finished in the previous visit will be continued in this visit. There is the possibility that a third day will not suffice, therefore, patients may return for a 4th and 5th baseline visit.

The anticipated time of this visit is 60-180 minutes.

6.3.6 Visit 4

- MRI scan/CT scan: those subjects who are able to undergo an MRI scan will be scanned on a 3T or 1.5T Siemens unit; if subjects are unable to undergo MRI they will have a CT scan of the head. If the subject is concerned about the potential for metal fragments in the head or body, we will offer an x-ray scan to check for foreign objects in the body. No contrast will be administered.
- In cases where the baseline visits will be conducted via tele-assessment, the Ruff Figural Fluency test may be administered at this visit.

The anticipated time of this visit is 120 minutes.

If genetic sampling was not able to be collected at baseline visits, it will be collected during Visit 4.

6.4 Phase 2 of the Study (Visits 5-14)

In the treatment phase, there will be 10 TMS sessions over 2 consecutive weeks in which 20 minutes (1200 pulses) of 1 Hz TMS at 90% MT will be delivered to the inferior pars triangularis. Each TMS treatment session will be immediately followed by a 60-90 minute session of CILT. On the first day of treatment, we will take the grip strength and finger flexibility motor measurements, as well as the 5th and 10th day. The total anticipated time of these visits will be 90-120 minutes.

6.4.1 AD Sub-Study Phase 2 (Visits 5-14)

In the treatment phase, there will be 10 TMS sessions over 2 consecutive weeks in which 30 two second trains of 10 Hz TMS will be delivered every 30 seconds at 100% MT to the left inferior pars triangularis and to the left posterior superior temporal gyrus. There will be a total of 600 pulses (30 trains x 2 seconds at 10 Hz) to each site in each session for a total of 1200 pulses per session. Each TMS treatment session will be immediately followed by a 60-90 minute session of CILT. The total anticipated time of these visits will be 90-120 minutes.

6.5 Follow Up Phase of the Study

6.4.1 Visit 15

- CILT Probe: this will assess the immediate effect of TMS + CILT on the treated words from CILT.

The anticipated time of this visit is 60 minutes.

The follow-up visit may be conducted via tele-assessment.

6.4.2 Visit 16 & 17 (3-month follow-up)

The same battery of tasks administered in visits 1 and 2 will be administered in these visits which will occur at 3 months after the end of TMS. The anticipated time of these visits is 120-180 minutes.

The 3-month follow-up visits may be conducted via tele-assessment.

6.4.3 AD Sub-Study Visit 16 & 17 (6-week follow-up)

The same battery of tasks administered in visits 1 and 2 will be administered in these visits, which will occur at 6 weeks after the end of TMS. The anticipated time of these visits is 120-180 minutes.

The 6-week follow-up visits may be conducted via tele-assessment.

6.4.4 Visit 18, 19 & 20 (6-month follow-up)

The same battery of tasks administered in visits 1 and 2 will be administered in these visits which will occur at 3 months after the end of TMS. The anticipated time of these visits is 120-180 minutes. Additionally, for those subjects who had an MRI at the beginning of the study, a repeat MRI scan will be performed using the same acquisition parameters described below. The ADRS will also be collected again at the 6-month follow-up timepoint. The ADRS is completed by the participant's caregiver.

The 6-month follow-up visits may be conducted via tele-assessment.

For in-person follow-up visits (i.e. not conducted via tele-assessment), the final day of the follow-up testing may include a brief tele-assessment, time permitting and with the subjects approval. This tele-assessment will consist of some combination of the tests (listed under Visits 1 and 2) conducted via video software; study personnel will conduct this tele-assessment from a nearby room.

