1.2.2.1 Time course of TMS Benefits

Evidence suggests that the benefit from TMS to the right IFG increases over time in the absence of ongoing therapy (10, 84, 86). We reported a similar finding in a subject followed for 10 months after TMS (47). As most studies assess treatment efficacy 2 months or less after treatment, there is reason to think that many studies reported to date (e.g., 1, 116, 127) have underestimated the benefit from TMS. Our proposed study will measure treatment-related outcomes at 3 and 6 months, with the expectation that the advantage for the TMS-treated group will be maximal at 6 months.

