3.1.3 Follow Up Phase

There will be two 3-month post-treatment visits and two 6-month post-treatment visits in which the full battery of language and cognitive assessments will be repeated. Subjects who are able to undergo MRI scanning will have anatomic and fMRI scans at or after the 6-month post-treatment visit.

All assessments listed are not mandatory. If the participant wishes to discontinue testing or refuses to perform a certain test due to frustration or fatigue, their request will be granted and not considered a deviation. Instead we will make note of any refused tests in our case report form (i.e. visit checklist).

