3.3 Study Endpoints

3.3.1 Primary Study Endpoints

The primary endpoint will be overall change in WAB-AQ between the first baseline visit and the 6 month follow-up visit

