8.1 Primary Endpoint

The primary endpoint will be overall change in WAB-AQ between the first baseline visit and the 6 month follow-up visit

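### The procedure for the 6-month visits, which supply the primary endpoint, dates them 3 months after TMS and so contradicts the rest of the protocol

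*Combined protocol and SAP*

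**What the plan says.** Section 3.3.1 defines the outcome: "The primary endpoint will be overall change in WAB-AQ between the first baseline visit and the 6 month follow-up visit". Section 8.1 repeats it for the statistical plan: "overall change in WAB-AQ between the first baseline visit and the 6 month follow-up visit". Section 1.2.2.1 explains the choice of time point, "with the expectation that the advantage for the TMS-treated group will be maximal at 6 months", and section 7.6 relies on the same expectation when it declines interim efficacy analyses.

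The visit procedures in section 6 then give two entries for the later follow-up of the main study. Section 6.4.2, for Visits 16 and 17 (3-month follow-up), refers to "these visits which will occur at 3 months after the end of TMS". Section 6.4.4, for Visits 18 to 20 (6-month follow-up), says that the battery "will be administered in these visits which will occur at 3 months after the end of TMS". Section 6.4.4 goes on: "The ADRS will also be collected again at the 6-month follow-up timepoint". Its tele-assessment sentence also calls these the 6-month visits.

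**The concern.** The procedure for the visits that produce the primary outcome gives a time that disagrees with the definition of that outcome. Anyone who schedules from the body of 6.4.4 would repeat the language battery at the time already used for Visits 16 and 17 and would obtain no WAB-AQ at 6 months.

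Two things depend on that measurement. The primary endpoint and the t-test used for the power calculation are both set at 6 months. The mixed model in 8.4.1 uses the 3-month and 6-month outcomes together, with an intervention-by-end-point interaction and a random end-point slope. If both end-points fall at the same time, neither term describes change between 3 and 6 months, and the expectation that the advantage is greatest at 6 months goes untested.

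**Working it through.** **Step 1. Timing statements for the last main-study assessment, side by side.**

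| Section | Time after TMS |
|---|---|
| 3.1 text and Figure 1 | 3 months, then 6 months |
| 3.1.3 | two 3-month visits, two 6-month visits |
| 3.3.1 and 8.1 (primary endpoint) | 6 months |
| 7.5 (test battery) | 3 and 6 months |
| 8.3 (power) | t-test at 6 months |
| 8.4.1 (mixed model) | 3 and 6 months together |
| 6.4.4 heading, ADRS and tele-assessment sentences | 6 months |
| 6.4.4 timing sentence for the battery | **3 months** |

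One sentence disagrees with all the rest, and it gives the same timing, in the same words, as 6.4.2.

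**Step 2. Total participation as a check on intent.** Section 7.5 allows up to 2 weeks for baseline and section 3.1.2 gives 2 weeks of treatment, about 0.9 month together. With a last visit at 6 months the total is about 0.9 + 6 = 6.9 months; with a last visit at 3 months it is about 0.9 + 3 = 3.9 months. Section 4.7 states 7-8 months, which fits only the 6-month reading.

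**Step 3. Does the visit number settle it?**

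| Event | Figure 1 | Section 6 |
|---|---|---|
| Baseline imaging | Visit 5 | Visit 4 |
| Treatment | Visits 6-16 | Visits 5-14 |
| Immediate CILT probe | Visit 17 | Visit 15 |
| 3-month follow-up | Visits 18-19 | Visits 16-17 |
| 6-month follow-up | Visits 20-22 | Visits 18-20 |

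Figure 1 counts screening as Visit 1, which shifts the numbers by 1. It also gives 16 − 6 + 1 = 11 numbers to the 10 treatment sessions, where section 6 gives 14 − 5 + 1 = 10, so the shift is 2 from the CILT probe onward. Looking up Visit 18 or 19 in Figure 1 therefore returns 3 months and appears to confirm the wrong sentence. The scan labels T5 and T22 in section 3.1 follow the Figure 1 numbering. The next entry, 6.4.5, uses Visits 18 to 20 again for the Alzheimer sub-study at 12 weeks, which is also close to 3 months.

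**Step 4. What a literal reading would do.** The last WAB-AQ would come 6 − 3 = 3 months early, half the intended follow-up. The gap between the two modelled end-points would go from 6 − 3 = 3 months to 3 − 3 = 0.

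**Step 5. Does any stated figure change?** Section 8.3 claims 80% power for 0.7 SD with 75 evaluable subjects allocated 2:1 (50 TMS, 25 sham) at alpha 0.05, taken here as two-sided.

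- Normal approximation: 0.7 / √(1/25 + 1/50) = 0.7 / 0.245 = 2.86; Φ(2.86 − 1.96) ≈ 81.5%.
- Two-sample t-test (noncentral t): 80.5%.
- Detectable difference: 0.7 × 5.7 = 3.99, the stated 4 points.

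The plan's figures reproduce, and they already refer to 6 months, so correcting 6.4.4 leaves them as they are. The documents give no effect size at 3 months, so the power of a misplaced assessment cannot be derived. Purely as an assumption, an effect of 0.5, 0.6 or 0.7 SD at that time would give t-test power of 52%, 68% or 81%.

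**The case against.** The strongest reply is that this is a slip with only one sensible reading. The sentence is correct in 6.4.2 and was evidently carried over. The heading of 6.4.4 and two of its other sentences say 6 months, as does every other main-study section on timing. Nothing gives section 6 precedence: section 3.1 points to Figure 1 for the overall timeline, and section 16 lists a procedures flowchart that is not part of the text reviewed. To lose the endpoint, staff would have to book visits titled as 6-month visits alongside the 3-month ones. All of this stands as to intent and likelihood, and it makes the point an inconsistency, not a flaw of design. It does not remove the contradiction, and Figure 1 resolves it only for a reader who goes by the column label and not by the visit number.

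Four stronger readings are tempting, and the documents do not support them:

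- *The protocol itself says that benefit is underestimated at 3 months.* Section 1.2.2.1 says this of studies that assess at 2 months or less. Three months is one of the trial's own planned assessments.
- *Visits 18 to 20 wholly duplicate Visits 16 and 17.* Only the timing and the test battery coincide. The repeat MRI and the ADRS are added in 6.4.4.
- *The final scan is undated.* Section 3.1.3 does say "Subjects who are able to undergo MRI scanning will have anatomic and fMRI scans at or after the 6-month post-treatment visit", but sections 3.1 (with Figure 1), 6.4.4 and 8.4.2 place the scan at the 6-month follow-up, and it serves a secondary objective.
- *The plan is wrong because it gives no visit window or tighter anchor.* Follow-up is already counted from the end of TMS. A window would add detail, but its absence is not an error in the passages at issue here.

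**Conclusion.** The point holds as an internal inconsistency in the timing of the primary-endpoint visits. Section 6.4.4 gives 3 months where the endpoint definition, design, battery, power calculation and mixed model all need a separate 6-month assessment. The size is conditional: for any subject scheduled from that sentence, the primary measurement is 3 months early and the two modelled end-points coincide. For a subject scheduled from the heading or the 6-month column of Figure 1, nothing is lost. A reader might infer that the trial plans to measure its primary outcome at the wrong time; the weight of the text is against that. No sample size or power figure is affected. The conclusion assumes that Figure 1's visit numbers are as extracted, which the T5 and T22 labels in 3.1 support. Correction is warranted because a protocol should not carry two times for its primary outcome.

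**What to change.** Reconcile 6.4.4 with 3.1, 3.1.3, 3.3.1, 7.5, 8.1, 8.3 and 8.4.1 by changing the interval in its timing sentence from 3 to 6 months, as the protocol's own endpoint definition requires. In the same amendment, align the visit numbers in section 6 with Figure 1, so that one number means one visit throughout. The cost is a wording amendment, with no added visits, subjects, procedures or analyses.
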